
Model Results Presentation
 
 As described above with Posterior Estimates, model parameters estimated from the Bayesian Emax model will be summarized through means, SD, median, MCSE/SD and equal-sided 95% credibility intervals. Median and 95% credibility intervals from Bayesian analyses and the model estimates and 95% CIs from frequentist analysis will be presented for MED, TD, and selected doses corresponding to the change of -0.25, 0.25, 0.5, 0.75 and 1 g/dL in Hgb from baseline. The Hgb dose response curve will be plotted as a line through the medians (of the predicted values of Hgb change from baseline on day 29 at a series of doses) and 95% credibility bands, and overlaid on a scatter plot of the observed data. A posterior probability distribution of predicted Hgb (g/dL) change over 29 days for each treatment group will be generated. A predictive posterior probability distribution of Hgb (g/dL) change over 29 days anticipated for a future subject, for each treatment group will be plotted. Density plots for each Emax parameter showing the prior and posterior distribution for the primary analysis overlaid with sensitivity priors analyses will be generated. A predictive posterior probability plot over the dose range to describe the probability that dose will maintain Hgb within the range of [-0.5, 0.5] g/dL after 29 days for a future subject will be generated. Dose ratios estimated by different approaches will be tabulated.

Additional Results Presentation
 
Listing of Hgb (and HemoCue Hgb data), Hgb change from baseline and Hgb derived parameters will be provided.

Analysis Datasets
 
 Unless otherwise specified, efficacy inference will be based on the ITT population using an observed case dataset, comprising of all non-missing data collected up to discontinuation of study drug and withdrawal from the trial. For dose response analysis based on ITT population, the analysis dataset comprises (1) all observed non-missing Hgb data collected up to Day 29; and (2) imputed Hgb value at Day 29 for subjects who have a Day 15 Hgb measurement but a missing Day 29 Hgb measurement.

Sensitivity and Supportive Statistical Analyses

To assess the robustness of the primary efficacy conclusions the dose-response analysis will be repeated using the sensitivity approaches described below.

- The primary dose-response model will be fitted based on the completer population. A table summarizing the results of these dose response analyses along with the dose response curve (alongside the primary analysis curve) will be produced on this population.
- The primary dose-response analysis will be repeated using the PP population if it comprises $\leq 80\%$ of the ITT population. A table summarizing the results of these dose response analyses along with the dose response curve (alongside the primary analysis curve) will be produced on this population.
- The dose-response Emax model will be fitted using alternative (weaker, less informative) prior distributions for the Emax model parameters. The results from this sensitivity prior analysis will be tabulated as previously described for the primary dose-response model.

Alternative Prior Distributions

Emax Model Parameters	Bayesian Priors
E0	\sim Normal (-1.2, $(1)^2$)
Emax	\sim Normal (5, $(3)^2$)
ED50	\sim Uniform (2, 200)
Tau ($1/\sigma^2$)	\sim Gamma (1,1)

- A 3-parameter frequentist Emax model will be fitted based on ITT population. It will be fitted using PROC NLMIXED or PROC NLIN, and will be presented as described above.
- A linear model will be fitted to the dose-response data based on ITT population, if a linear relationship looks plausible across the three-times weekly dose range and will be presented as described above. This analysis will be repeated in the Completers and Per Protocol populations.

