9.2. Sample Size Considerations

No formal sample size and power calculations were performed because the focus of this study is on characterizing the Hgb-three-times weekly dose-response relationship and using the results to estimate the dose ratio between three-times weekly and QD doses that produce the same Hgb response, not on formal testing of hypotheses. A sample size of approximately 90 randomized subjects has been determined based on feasibility (18 per arm).

Assuming a maximum dropout rate of 15% between randomization and Day 29, it is anticipated that approximately 75 subjects will complete 29 days treatment.

Subjects will be stratified by prior ESA dose (low, high), and then randomized in equal proportions to receive placebo three-times weekly, or GSK1278863 dose of 10 mg three-times weekly, 15 mg three-times weekly, 25 mg three-times weekly, or 30 mg three-times weekly.

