9.4. Key Elements of Analysis Plan

The analyses planned in this protocol will be expanded upon in the RAP, any subsequent deviations will be explained either in the RAP or the final study report as appropriate.

Demographics, all baseline characteristics and subject withdrawals (from IP and study) will be summarized.

The impact of key (pre-defined) baseline subject characteristics and covariates of specific clinical interest on the primary Hgb endpoint (and potentially other key PD endpoints) will be explored.

Baseline characteristics and clinical covariates include:

- Baseline Hgb
- Prior ESA dose (high, low)
- Weight
- Gender

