Once the dose response model has been fitted satisfactorily, the posterior distribution of the model parameters (E0, Emax, ED50, and variance) will be summarized through means, standard deviation, median, MCSE, MCSE/SD and equal-sided 95% credibility intervals. The predicted value at a series of doses (range of possible doses from 0 to 30 will be sectioned off into a sequence of 1 increments; i.e. dose levels of 0, 1.0, 2.0, ..., 30.0.) will also be monitored and the median and 95% credibility values obtained at each dose. The Hgb dose response curve will be plotted as a line through these medians and 95% credibility bands, and overlaid on a scatter plot of the observed data. This estimated dose response curve is a composite best fit at each dose and is not in itself an Emax curve.

The dose response model will be used to make the primary efficacy inferences as described in Section 9.1.

To assess the robustness of the primary efficacy conclusions the dose-response analysis will be repeated using the following sensitivity approaches:

- excluding subjects who fail to complete 29 days of treatment (completers population)
- using alternative (weaker) prior distributions for the Emax model parameters (prespecified in the RAP)
- fitting a Frequentist Emax model to the dose-response data (if possible to fit the model)

• fitting a linear model to the dose-response data, if a linear relationship looks plausible across the three-times weekly dose range

If problems are encountered fitting a three parameter Emax model or if the Emax shape is a poor fit for the data, alternative models will be investigated until an appropriate model can be chosen (i.e. power model, linear model, quadratic model, log-transformed dose *et al.*). Full details for model selection will be provided in the RAP.

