7.1.2. Planned Hgb Efficacy Statistical Analyses

Primary Statistical Analyses
Endpoint(s)

 • Hgb change from baseline at Day 29
Model Specification

 • The primary endpoint is change in Hgb from baseline at Day 29. To model the dose-response relationship a three-parameter Emax model is planned, where Emax is assumed an appropriate model based on the biology and QD-dose-response modeling completed to date for GSK1278863. 
This model assumes the following form:
 $\Delta Hgb = E0 + \frac{(Emax - E0)}{1 + \left(\frac{ED50}{dose}\right)} + \epsilon$ 
Where:
 
 • ΔHgb is the change in Hgb from baseline at Day 29 • E0 is the placebo response • Emax is the maximum response

Primary Statistical Analyses											

 ED50 is the dose that attains the intermediate response, i.e. where $(E_0 + E_{max}) / 2$, is attained ϵ is a random error assumed to be normally distributed with mean zero and constant variance (σ^2) 
The observed change in Hgb from baseline at Day 29 will be used as the response variable in the Emax model. Subjects who have a Day 15 Hgb measurement but a missing Day 29 Hgb measurement will be included with a Day 29 value imputed (see Section 11.7.2.1). Any subject who prematurely discontinues dosing prior to Day 15 will be non-evaluable for the dose-response analysis.
											
Prior Distribution											

The Emax model will be fitted using Bayesian statistical methods (i.e. a posterior Emax model). Prior distributions for each of the model parameters have been based on the estimates obtained from GSK study PHI113633. This modeling provides confidence in setting prior distributions for E0, however, there is greater uncertainty in the estimation of Emax and ED50, which will be explored in sensitivity analyses with alternative (weaker) prior distributions.
											

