- A predictive posterior probability plot over the dose range to describe the probability that dose will maintain Hgb within the range of [-0.5, 0.5] g/dL after 29 days for a future subject. This plot will be used to determine the probability of a future subject achieving Hgb in [-0.5, 0.5] range at each dose. By comparing across doses, evidence will be provided for the expected improvement of one dose over another, and may aid selection of titration doses in phase 3.

Additional Dose Response Modeling

A Frequentist 3-parameter Emax model in the model form defined as above will also be fitted to data. The derived data from this Emax model (estimates of E0, Emax, ED50 and Var along with their standard error, and 95% CI) will be tabulated and a dose-response curve (alongside the primary analysis curve and sensitivity prior analysis) will also be produced.

Primary Statistical Analyses											

If problems are encountered fitting a three parameter Emax model, or if the Emax shape is a poor fit for the data, or a linear relationship looks plausible across the three-times weekly dose range, then a linear model will be considered of the form:
 $\Delta Hgb = E0 + \alpha Dose$ 
Other appropriate models, such as quadratic model and log-transformed dose will also be explored if necessary.
											
Dose Response Exploration											

 A scatter plot will be produced by study with total weekly doses as x-axis, and Hgb responses as y-axis including the combined QD (PHI113633 excluding Japan) and three-times weekly (204836) data. The pattern can be examined to explore whether or not the two regimens with the same weekly dose would have the same response. 											
Dose Ratio Estimation											

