8.1.2. Planned Efficacy Statistical Analyses

Secondary Statistical Analyses
Endpoint(s)

 Hgb change from baseline at Day 29
Model Specification

 Repeated Measures Analysis of Hgb Change from Baseline 
The observed change in Hgb from baseline to Day 29 will be analyzed by a repeated measures model using the PROC MIXED procedure. Hgb data will be used from Day 15 and Day 29 provided it is collected on-treatment; a subject must have a baseline value and at least one on-treatment Hgb assessment to be included in the analysis. Model effects will include baseline Hgb, treatment, time, and treatment-by-time interactions. The estimation method to use will be Restricted Maximum Likelihood (REML). The Kenward and Roger version of the F-test will be used. The variance-covariance structures for repeated measures within the same subject will be unstructured (UN). For Day 29, least squares mean differences will be calculated as estimates of the difference between the GSK1278863 groups and placebo, together with 95% CIs. These results will be tabulated.
 Subgroup Analysis 
The observed change in Hgb from baseline to Day 29 by subgroups will be analyzed by a repeated measures model using the PROC MIXED procedure. The subgroups of interest are detailed in Section 11.10.1 In order to analyse a particular subgroup, at least 30% of total ITT subjects will be required in each subgroup (approximately 27 subjects per subgroup anticipated). Hgb data will be used from Day 15 and Day 29 provided it is collected on-treatment; a subject must have a baseline value and at least one on-treatment Hgb assessment to be included in the analysis. Model effects will include baseline Hgb, treatment, time, subgroup, treatment-by-time, treatment-by-subgroup, subgroup-by-time and treatment-by-time-by-subgroup interactions. The estimation method to use will be Restricted Maximum Likelihood (REML). The Kenward and Roger version of the F-test will be used. The variance-covariance structures for repeated measures within the same subject will be unstructured (UN). For Day 29, the least squares mean differences will be calculated as estimates of the difference between each GSK1278863 treatment group and placebo for each subgroup, together with 95% CIs. All comparisons will be presented, irrespective of the number of subjects per treatment arm within each subgroup.
 
Note: if subgroup is baseline Hgb (<10 vs. >=10 g/dL), drop the continuous variable for baseline Hgb from the model.

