11.10. Appendix 10: Examination of Covariates and Subgroups

11.10.1. Handling of Covariates and Subgroups

- The following is a non-exhaustive list of covariates that may be used in descriptive summaries and statistical analyses, some of which may also be used for subgroup analyses (See Section 8.1.1 and Section 8.1.2 for further details).
- Additional covariates of clinical interest may also be considered.
- If the percentage of subjects is small within a particular subgroup, then the subgroup categories may be refined prior to unblinding the trial.

Category	Covariates and / or Subgroups
Baseline Hgb	<10, >=10 g/dL
Weight	<=Median, >Median kg
Body Mass Index (BMI)	<27, 27 to <30, >=30 kg/m ²
Type of Prior ESA	Epoetin IV, Darbepoetin, Mircera
Standardized Prior rhEPO dose	standardized dose by tertile (<=xx.xx, >xx.xx and < xx.xx, >=xx.xx)
Prior ESA dose (stratification factor)	Low ESA dose: <100 IU/kg/week epoetin OR <0.5 µg/kg/week darbepoetin OR <0.6 µg/kg/week methoxy PEG-epoetin beta High ESA dose: ≥100 IU/kg/week epoetin OR ≥0.5 µg/kg/week darbepoetin OR ≥0.6 µg/kg/week methoxy PEG-epoetin beta
Ethnicity	Not Hispanic or Latino, Hispanic or Latino
Race	White, African American, Asian, Other
Gender	Male, Female
Age	<65, >=65 to < 75, >=75 years
Region	North America, Europe
Diabetes	Yes, No
Phosphate Binders	Yes, No
Baseline Absolute Reticulocyte Count	<= Median, >Median TI/L

NOTES :

- Subgroup summaries will only be produced if there are at least 30% of total ITT subjects in each subgroup.

11.11. Appendix 11: Multiple Comparisons & Multiplicity**11.11.1. Handling of Multiple Comparisons & Multiplicity**

No adjustment for multiplicity will be made because (1) all statistical analyses are estimation based, and (2) the focus of this study is on characterizing the Hgb-three-times weekly dose-response relationship and using the results to estimate the dose ratio between three-times weekly and QD doses that produce the same Hgb response, not on formal testing of hypotheses.

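### The dose-response models behind TD, MED and the dose ratio contain dose only; adding baseline Hgb and the prior ESA stratum would give a modest, almost free gain in precision

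*SAP*

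**What the plan says.** - **Primary model.** SAP 7.1.2 and Protocol 9.4.1.1 give a three-parameter Emax model in dose with a normal error. In the SAP's words, "The observed change in Hgb from baseline at Day 29 will be used as the response variable in the Emax model". TD, MED and the other response-specific doses are computed from its parameters.
- **Other dose-response models.** The frequentist Emax model has the same form. If the Emax fit is poor or a straight line looks plausible, "then a linear model will be considered of the form" E0 plus a slope times dose. The dose ratio uses these models and the same models refitted to PHI113633.
- **Sensitivity analyses.** Protocol 9.4.1.1 says: "To assess the robustness of the primary efficacy conclusions the dose-response analysis will be repeated using the following sensitivity approaches". Its list, together with SAP 7.1.2, covers completers, per protocol, weaker priors, frequentist Emax and linear. None adds a covariate.
- **Design and stated interest.** Protocol 9.2: "Subjects will be stratified by prior ESA dose (low, high), and then randomized in equal proportions". Protocol 9.4 says that "The impact of key (pre-defined) baseline subject characteristics and covariates of specific clinical interest on the primary Hgb endpoint" will be explored, and lists baseline Hgb, prior ESA dose, weight and gender.
- **Where covariates do appear.** In the repeated measures analysis of SAP 8.1.2, "Model effects will include baseline Hgb, treatment, time, and treatment-by-time interactions"; the stratum is not among them. The stratum can enter the subgroup version, subject to a condition: "In order to analyse a particular subgroup, at least 30% of total ITT subjects will be required in each subgroup". Neither model feeds TD, MED or the dose ratio. SAP 11.10.1 lists covariates that may be used, but refers to 8.1.1 and 8.1.2, not to 7.1.2.

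**The concern.** The study tests no hypothesis, so the width of the intervals for TD, MED and the dose ratio is what it delivers. About 75 evaluable subjects support them, and Protocol 9.2.1 itself calls the precision relatively low. Two baseline variables that may predict Hgb change are already held. One is the stratification factor: the design balances it across arms, but a dose-only model leaves its variance in the residual. The exploratory repeated measures model adjusts for baseline Hgb while the primary model does not, and the SAP's table of changes from the protocol gives no reason. What is at stake is interval width that could be recovered without extra subjects or data.

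**Working it through.** **Inputs.** Protocol 9.2.1: N = 75, E0 = -0.666, Emax = 5.258, SD of change 1 g/dL, ED50 37.28 or 78 mg. Protocol 4.2 and 4.3: doses 0, 10, 15, 25, 30 mg, 15 evaluable per arm. SAP 7.1.2 priors: E0 ~ N(-0.67, 0.146^2), Emax ~ N(5.26, 1.337^2), ED50 ~ U(10, 120), tau ~ Gamma(1, 1). R2, the share of within-arm variance explained by the two covariates, is not in the documents and is assumed to be 0.1, 0.2 or 0.3.

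**1. Reproduce the plan's Table 4.** The dose giving response y is ED50(y - E0)/(Emax - y).
- TD (y = 0): 37.28 x 0.666/5.258 = 4.72 mg, or 78 x 0.666/5.258 = 9.88 mg.
- The delta method uses covariance SD^2(J'J)^-1 from the dose-only Emax model, times 1.96. It gives TD half-widths of 2.85 and 5.93 and MED half-widths of 2.84 and 5.33. Table 4 has 2.86, 5.94, 2.85 and 5.34.

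The stated precision is therefore that of an unadjusted, prior-free model.

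**2. Frequentist gain.** Residual variance becomes 1 - R2, so half-widths scale by sqrt(1 - R2) = 0.949, 0.894, 0.837. They fall by 5, 11 and 16%, as if 75/(1 - R2) = 83, 94 or 107 subjects had been analysed unadjusted.

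For the linear slope (0.05, SDx 10, SDy 1) the half-width is t x SDy x sqrt(1 - r^2)/(SDx x sqrt(df)), with r = 0.5. With 73 df this is 0.0202, against 0.020 in Table 5. With two more df spent it becomes 0.0194, 0.0183 and 0.0171 (4, 9 and 15% narrower). At R2 = 0 it is 0.0205, about 1.4% wider. A sample R2 near 0.03 cancels that, and two irrelevant covariates would reach about 2/73 = 0.027 by chance.

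**3. Bayesian gain, approximate.** Adding prior precisions 1/0.146^2 and 1/1.337^2 for E0 and Emax, at R2 = 0, 0.1, 0.2, 0.3:
- TD: 1.69, 1.65, 1.60, 1.55 (ED50 37.28); 3.20, 3.07, 2.94, 2.80 (ED50 78).
- MED: 1.48, 1.45, 1.43, 1.39; and 2.90, 2.85, 2.79, 2.72.

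**4. Bayesian gain with all four SAP priors.** Given ED50 and tau, the model is linear and normal in the remaining parameters, so the posterior can be computed on an ED50 by tau grid. There were 300 simulated trials per cell, with the stratum balanced within arm, R2 split equally between the covariates, and N(0, 10^2) priors on their coefficients. Mean 95% half-widths in mg, unadjusted to adjusted, with the gain taken before rounding:

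| R2 | TD, ED50 37.28 | TD, ED50 78 | MED, ED50 37.28 | MED, ED50 78 |
|---|---|---|---|---|
| 0.1 | 1.73 to 1.68 (2.8%) | 3.40 to 3.28 (3.7%) | 1.60 to 1.57 (1.7%) | 3.11 to 3.06 (1.7%) |
| 0.2 | 1.74 to 1.65 (5.4%) | 3.38 to 3.11 (7.9%) | 1.61 to 1.56 (3.7%) | 3.08 to 2.96 (3.8%) |
| 0.3 | 1.73 to 1.58 (8.5%) | 3.39 to 2.97 (12.6%) | 1.59 to 1.50 (5.7%) | 3.07 to 2.87 (6.6%) |

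The simulation standard errors are 0.2 to 0.35 percentage points. At R2 = 0 the change is -0.3% and +0.1% for TD and -0.4% and 0.0% for MED (negative means wider).

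**5. Break-even.** Interpolating TD at ED50 37.28 between -0.3% at R2 = 0 and +2.8% at 0.1 gives 0.1 x 0.3/3.1, about 0.01. At R2 = 0.03 the TD gain is already about 1%.

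**6. Is R2 of 0.1 to 0.3 plausible?** A uniform spread over the 9.0 to 11.5 g/dL entry range has SD 2.5/sqrt(12) = 0.72. An assumed slope of change on baseline of -0.3 to -0.7 gives R2 = (0.3 x 0.72)^2 = 0.05 to (0.7 x 0.72)^2 = 0.25 from baseline Hgb alone. The narrow entry range and the two-visit averaged baseline may lower it.

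**The case against.** The best defence is that nothing here is an error. Protocol 9.4 promises to explore the covariates, not to adjust the dose-response model, and the subgroup models of SAP 8.1.2 do explore them. That stands: a reader might infer that the SAP breaks a protocol commitment, and it does not.

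The gain is also small and rests on an assumed R2. At R2 = 0.1 the Bayesian TD half-width falls by 0.04 or 0.13 mg in the approximation of step 3, far below the smallest active tablet (5 mg, Protocol 6.1). The 5, 11 and 16% figures belong to a sensitivity fit, not the primary one. Protocol 9.2.1 attributes the low precision at least partly to ED50 lying outside the dose range, which covariates do not cure. All this stands and is why the gain is called modest.

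Finally, dose-only models match those fitted to PHI113633, whose estimates inform the priors. That is a good reason to keep the dose-only fit, but not a reason to omit an adjusted one. With covariates centred at this trial's means, E0 is still the average placebo response here, so its prior fits no worse than before.

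A stronger reading is that differences in baseline Hgb or ESA mix between the studies distort the dose ratio and mimic dose dependence. The documents show no such difference. If a 0.1 g/dL shift is simply assumed, then under the SAP priors a true ratio of 2.33 moves to about 2.1 or 2.6 and stays nearly flat from 0 to +1 g/dL. That move of 0.2 to 0.3 is smaller than the Bayesian sampling half-width of 0.75 to 0.83 at 0 g/dL, with the QD dose treated as known. SAP 7.1.2 also bases the conversion decision on several approaches together.

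**Conclusion.** The omission is clear in the text and its cost is modest. For an assumed R2 of 0.1, 0.2 and 0.3, adjustment narrows the primary Bayesian TD interval by about 3, 5 to 6 and 8 to 9% (ED50 37.28) or 4, 8 and 12 to 13% (ED50 78), and the MED interval by about 2, 4 and 6%. Break-even in that fit is at an R2 of about 0.01 or less, so the change has little downside. The figures rest on additive covariate effects, 15 evaluable subjects per arm and the Protocol 9.2.1 parameter values; the unknown R2 drives the size.

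A reader might infer that the unadjusted TD and MED are biased. They are not on this account: arms are randomized within strata, so the omission affects width only. This is an improvement worth making, not a flaw that invalidates the planned analysis.

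**What to change.** Before unblinding, amend SAP 7.1.2 and 8.1.2 as follows.

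- Add centred baseline Hgb and prior ESA stratum (as randomized, from IVRS) as additive terms in the Bayesian Emax, frequentist Emax and linear models, with vague normal priors on the two coefficients in the Bayesian fit.
- Read TD, MED and the other response-specific doses at the mean covariate values, and state the centring at which the E0 prior applies.
- Average the future-subject predictions over the covariate distribution.
- Report the dose-only fits alongside, because the E0 prior and the PHI113633 comparison come from dose-only models.
- Add the stratum to the main repeated measures model.
- At most, tabulate baseline Hgb and ESA mix for the two studies side by side as context for the dose ratio.

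The cost is two extra parameters, a centring choice and a little more programming. No further data from this trial are needed. The documents do not say whether PHI113633 holds an equivalent stratum, and the change does not depend on it.
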